8.0 STUDY CALENDAR

* all screening and study visits have the option of being virtual depending on clinic requirements due to pandemic status or natural disasters

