3.4 Patient Exclusion Criteria

- Prisoners are excluded from participation
- There is **NO** exclusion criteria pertaining to ECOG performance status, laboratory values, prior cancer diagnoses, presence of comorbidities or brain metastases.

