4.2 Physical Therapy Intervention

The Physical Therapy Intervention will include a total of 12 weeks with one PT visit per week virtually or in-person depending on in-person clinic limitations due to pandemic or natural disasters. Week 1 assessment will be during an in-person visit with physician team within the OSU Brain and Spine Hospital. The other weekly visits will occur through virtual health monitoring at the best availability of the patient and Physical Therapist. There will be a final visit during week 13 where participants undergo the same assessments as the baseline visit as a routine usual care physical therapy discharge visit. The VH visits will be billed as research or as standard-of-care depending on insurance reimbursement changes for VH visits.

The exercise intervention will begin with a 10 minute warm-up using a portable exercise peddlers either using the patient's feet or arms, depending on their mobility and pain status. For example, if the patient is non-ambulatory and does not have the use of their legs, they will be instructed in peddler use with their arms. The Core exercises will include; seated posterior pelvic tilts and seated without back support seated marches. The resistance training exercises will include shoulder press, tricep extension, bicep curls, upper extremity side raises, chest press, calf raises, marches, standing side leg lifts, leg extension in standing, seated knee extension and clamshells. These will be done in 2 sets of 10 reps using resistance bands appropriate for patient's level of fitness. The cool-down portion will include stretches targeting upper extremities (chest, shoulders, and triceps), lower extremities (calves, quadriceps, and hamstrings) and trunk. Each stretch will be held for 30 seconds each. At week 1 visit patient will receive exercise packet including handouts for above therapeutic exercises three resistance bands (yellow, red and green) in order to progress resistance at home based on patient feedback. The physical therapist will educate and demonstrate appropriate use of the equipment during virtual visits or in-clinic visits depending on encounter type. In order to evaluate how hard the participant is working during the virtual health visits; the relative perceived effort (RPE)¹⁶ will

be used with a target goal of 12-14 on the Borg Rating Scale.¹⁷ This indicates a moderate level of intensity.

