An exercise log in the patient's electronic medical record will be filled out after each workout to keep track of patient progress. The patient will first be prescribed weekly sessions, then it will increase to twice weekly, then three times weekly based on patient behavior and activity tolerance. One session per week will be supervised virtually or in-person by the physical therapist. Additional sessions will be done by the patient on their own per standard-of care physical therapy practice. During the virtual health sessions, the physical therapist will assess barriers to doing their physical therapy and will problem solve with the patients on how to improve adherence. Please see [Appendix B] for a detailed description of the study exercise log.

Physical Therapy Safety Procedures

Upon the initial in-person visit the physician team or physical therapist will perform a standard-of-care safety screening of pulse oximetry assessment, heart rate and blood pressure monitoring, asking if patient has cardiac or pulmonary history. This screening will take into account if the patient is on oxygen, wears glasses or hearing aids. The in-person visit will also determine the location of the VH physical therapy, their emergency contact, and will verify their home address. It will be recommended that the patient perform their physical therapy in the same location each time. The physical therapist will perform a VH safety checklist at the beginning of each session. This checklist may include but not limited to the following questions:

- Where are you currently located?
- Is anyone else home with you?
- Is your cell phone charged and located near you?
- Have you had any new or different chest pain in the last week?
- Have you had any new or different shortness of breath in the last week?

During the VH visits, similar to an in-person visit, if the patient experiences any sudden chest pain or shortness of breath, they will be instructed to stop the activity, sit-down, and call their emergency contact within the home. If they are unable to call for help or are home alone, the physical therapist will call 911 and will notify the treating physician.

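### Under pandemic or disaster conditions the calendar footnote allows Visit 1 to be virtual, while section 4.2 ties the measured safety screen before home exercise to an in-person first visit

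*Combined protocol and SAP*

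**What the plan says.** Two parts of the protocol set the mode of the first visit.

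- **Section 8.0, Study Calendar, footnote:** "all screening and study visits have the option of being virtual depending on clinic requirements due to pandemic status or natural disasters". The calendar includes a Visit 1 (Baseline) column, with Physical Exam and Vital Signs marked in it. The footnote does not except that column.
- **Section 4.2, Physical Therapy Intervention:** "Week 1 assessment will be during an in-person visit with physician team within the OSU Brain and Spine Hospital". The sentence before it allows the weekly therapy visits to be virtual or in person, depending on pandemic or disaster limits on the clinic. The sentence after it sends the remaining weekly visits to virtual health.

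The safety procedures in section 4.2 then depend on that first visit:

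- "Upon the initial in-person visit the physician team or physical therapist will perform a standard-of-care safety screening of pulse oximetry assessment", continuing with "heart rate and blood pressure monitoring, asking if patient has cardiac or pulmonary history".
- "The in-person visit will also determine the location of the VH physical therapy, their emergency contact, and will verify their home address".

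For virtual sessions, section 4.2 adds a checklist led by the therapist at the start of each session, and section 4.18 repeats this. The listed items are questions about current location, company at home, the phone, and new chest pain or breathlessness. The list is expressly open-ended.

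**The concern.** If the footnote governs Visit 1, the occasion to which section 4.2 assigns the oximetry, heart-rate and blood-pressure readings no longer exists in the form described, and the protocol names no substitute. A site working under restrictions would have one rule saying the first visit may be virtual and another saying it is in person, with nothing to say which prevails.

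What is at stake is participant safety and consistent conduct. Participants are at least 60 years old with advanced lung cancer. Section 3.4 states that there is no "exclusion criteria pertaining to ECOG performance status, laboratory values, prior cancer diagnoses, presence of comorbidities or brain metastases", so the eligibility criteria do not act as a physiological screen. The exercise target is moderate intensity, and section 4.2 allows progression to further sessions that patients do by themselves. The emergency procedure in the same section relies on an emergency contact, and the plan assigns its collection to the same in-person visit.

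**Working it through.** No arithmetic applies. The plan states no figure on this point, and the question is whether its rules agree. I set the relevant text side by side.

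**Step 1. Does the footnote reach the first visit?** Its words cover all screening and study visits and name no exception. It is conditional on clinic requirements arising from a pandemic or natural disaster. Within that condition, Visit 1 is included as written.

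**Step 2. Is calendar Visit 1 the same visit as the Week 1 assessment?** The protocol does not say so in terms. Section 4.2 describes a week 13 visit that repeats the baseline assessments, and the calendar has Visit 1 as baseline and Visit 5 at 13 weeks. I therefore take Week 1 and Visit 1 to be the same visit. This is an inference.

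**Step 3. Is a fully remote start provided for elsewhere?** Largely, yes.

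| Element | Remote provision | Section |
|---|---|---|
| Consent | Telephone, with electronic signature | 3.5 |
| Pedal exerciser and bands | May be mailed home | 4.1 |
| SPPB | Physical therapist may administer it virtually, with fall precautions | 4.4 |
| Walk test | Done only if therapy is in person | 4.5 |
| Oximetry, heart rate, blood pressure screen | None stated | 4.2 |
| Exercise location, emergency contact, address | Assigned to the in-person visit; no remote version stated | 4.2 |

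The authors dealt with remote conduct for consent, equipment and physical testing. The last two rows have no such provision.

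**Step 4. Does anything else supply the measured readings?**

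- The session checklist lists questions and no measurements. Its symptom items ask about change over the past week, so they give no resting reading.
- The Visit 1 entries for Physical Exam and Vital Signs could capture heart rate and blood pressure, but they fall under the same footnote and no remote method is described.
- Readings taken at treatment visits might exist, but the protocol does not link them to clearance for exercise.

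**Step 5. What remains if Visit 1 is virtual?** Physician referral (3.2), medical and cancer history at screening (calendar), the verbal checklist before each therapy session (4.2, 4.18), intensity guided by perceived effort (4.2), and the stop-and-call procedure with emergency services as back-up (4.2). Cardiac and pulmonary history, contact details and address can all be taken by voice. The part without a stated route is the three measured readings.

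**Step 6. How many patients?** The documents give no rate of virtual first visits. The lower bound is zero. The upper bound is everyone enrolled, which is 20 in section 3.1 and 30 in section 6.1. These are bounds only and estimate nothing.

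**The case against.** The strongest reply is that section 4.2 already takes account of pandemics and still keeps Week 1 in person. The sentence allowing virtual weekly visits comes directly before the one fixing the Week 1 assessment as in person, and only the other weekly visits are then sent to virtual health. A specific rule next to the pandemic clause can be read as an exception to a general footnote. The asterisk is also attached to the calendar's assessment heading, and the calendar has no row for therapy sessions or the therapy safety screen. The footnote may therefore concern only how study assessments are delivered.

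This reading is plausible, but the protocol does not state it. The footnote speaks of visits as well as assessments, and nothing gives section 4.2 precedence. The objection lowers the likelihood that a site would skip the screen, but it does not remove the conflict.

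A second reply is that many patients would be in the clinic for treatment anyway. Section 3.1 builds in-person sessions into routine treatment visits, and section 4.12 describes blood drawn around sessions. That stands as a reason why few may be affected. It does not say who takes the readings, or that they reach the therapist before exercise starts.

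A third reply is that the analysis is unaffected. That is correct: baseline vital signs enter none of the endpoints in section 6. The screen is called standard of care and has no stated threshold or action, so how heavily the plan relies on it is partly inferred.

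**Conclusion.** The conflict holds. Under pandemic or disaster conditions the calendar footnote permits a virtual Visit 1, while section 4.2 requires an in-person Week 1 assessment and attaches the measured safety screen and the emergency details to it. If the footnote is followed as written, home exercise could start without the oximetry, heart-rate and blood-pressure readings. It should be corrected because it touches participant safety and a short edit resolves it. It is not a flaw in the analysis.

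The conclusion rests on two assumptions: that Visit 1 and the Week 1 assessment are the same visit, and that the footnote is not silently overridden by section 4.2. The number affected is unknown and may be zero.

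A reader might infer more than the documents support:

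- **That patients could start entirely unscreened, with no other check.** Referral, history-taking and the open-ended checklist at each session all remain.
- **That none of the three readings could be obtained remotely.** The equipment description is not presented as exhaustive, and a pulse can be counted without a device. What the text shows is that no method is described.
- **That the emergency details would be lost.** They can be collected by voice, and the checklist asks the current location each time. Only their assigned occasion is missing.

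**What to change.** Reconcile section 4.2 (the Week 1 sentence and the safety procedures) with the section 8.0 footnote and the Visit 1 entries for Physical Exam and Vital Signs. The text should state one of two things:

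1. that the Week 1/Visit 1 safety screen is outside the virtual option; or
2. how the readings named in section 4.2 are obtained and recorded before the first exercise session when that visit is virtual.

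The same edit should say when exercise location, emergency contact and home address are recorded in that case. Which clinical rule applies is for the sponsor to decide.

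Optionally, add a record that the screen and the emergency details are on file before the first session. The contradiction can be resolved without it.

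The cost is a few sentences of protocol text and, if the optional record is adopted, one extra data field. The downside is that some patients may start later while the clinic is restricted.
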